15.4.2.1. Treatment States for AE Data

For adverse events, partial AE start date will use imputation as described in Section 15.7.2.1. In the case of a completely missing start date, the event will be considered to have started On-treatment in the Maintenance phase unless an end date for the AE is provided which is before start of study treatment at Maintenance phase; in such a case the AE is assigned as Pre-treatment.

Additional variables will be derived as shown in Table 17.

Table 17 Days since First Dose of Each Study Phase, Days since Phase Start, AE Duration and Relation to Study Treatment

	Definition
Days since First Dose (Days) ^a	AE Start Date – Maintenance Treatment Start Date + 1
Days since Last Dose (Days) ^a	AE Start Date – Date of Last Dose of Study Treatment prior to/on the Start Date of AE + 1
Days since Phase Start	
For AEs in Maintenance Phase: AE Start Date - Maintenance Treatment Start Date + 1
 
For AEs in Extension Phase: AE Start Date – Date of Nominal Week 100 Visit + 1
 
For AEs in Long-term Follow-up Phase: AE Start Date – Date of Last Dose of Study Treatment^b

Duration (Days)	AE Resolution Date – AE Start Date + 1
Drug-related	If relationship is marked 'YES' on Inform/eCRF or value is missing.

NOTES:

- Days since First/Last Dose will only be derived for AEs assigned to maintenance phase, extension phase and long-term follow-up phase.
- Date of Last Dose of Study Treatment = max (Last IM Injection Date, Last Oral Bridging End Date), only applicable to participants who permanently discontinued study treatment.

15.4.3. Study Period

Certain displays will be produced for data collected during the oral lead-in. The study period variable is defined in Table 18 and Table 19. Study period is assigned after the study phase is assigned (screening, maintenance, extension, or long-term follow-up) based on the Tables in Section 15.4.1.

Table 18 Assignment of Study Period for AE Data

Study Period	Date range
Oral Lead-in	
For participants receiving at least one Injection: Maintenance Treatment Start Date \leq Date < Date of First IM Injection
 
For participants withdrawing prior to first Injection: Date \geq Maintenance Treatment Start Date
 
Note that the oral lead-in period is only applicable to the participants who received at least one dose of study treatment during the oral lead-in period in the study. Oral lead-in period is within the maintenance phase.

NOTES:

- Date = AE Start date.

Table 19 Assignment of Study Period for Lab Assessments:

Period	Date range
Oral Lead-in	
For participants receiving at least one Injection: Maintenance Treatment Start Date < Date \leq Date of First IM Injection
 
For participants withdrawing prior to first Injection: Date > Maintenance Treatment Start Date
 
Note that the oral lead-in period is only applicable to the participants who received at least one dose of study treatment during the oral lead-in period in the study. Oral lead-in period is within the maintenance phase.

NOTES:

- Date = Date of assessment.

15.5. Appendix 5: Data Display Standards & Handling Conventions

15.5.1. Reporting Process

Software	

 The currently supported versions of SAS software will be used. 	
Reporting Area	
HARP Server	: us1salx00259
HARP Compound	: \ARPROD\GSK1265744\mid207966
Analysis Datasets	

 Analysis datasets will be created according to CDISC standards (SDTM IG Version 3.2 & ADaM IG Version 1.0). For creation of ADaM datasets (ADCM/ADAE), the same version of dictionary datasets will be implemented for conversion from SI to SDTM. 	
Generation of RTF Files	

 RTF files will be generated for every reporting effort described in the RAP. 	

15.5.2. Reporting Standards

General	

 The current GSK Integrated Data Standards Library (IDSL) will be applied for reporting, unless otherwise stated (IDSL Standards Location: https://spope.gsk.com/sites/IDSLLibrary/SitePages/Home.aspx): 
 4.03 to 4.23: General Principles 5.01 to 5.08: Principles Related to Data Listings 6.01 to 6.11: Principles Related to Summary Tables 7.01 to 7.13: Principles Related to Graphics 	
Formats	

 GSK IDSL Statistical Principles (5.03 & 6.06.3) for decimal places (DP's) will be adopted for reporting of data based on the raw data collected, unless otherwise stated. Numeric data will be reported at the precision collected on the eCRF. The reported precision from non eCRF sources will follow the IDSL statistical principles but may be adjusted to a clinically interpretable number of DP's. 	
Planned and Actual Time	

 Reporting for tables, figures and formal statistical analyses: 
 Actual time relative to dosing will be used in figures, summaries, statistical analyses and calculation of any derived parameters, unless otherwise stated. The impact of any major deviation from the planned assessment times and/or scheduled visit days on the analyses and interpretation of the results will be assessed as appropriate. Reporting for Data Listings: 
 If space allows, planned and actual time relative to study drug dosing will be shown in listings (Refer to IDSL Statistical Principle 5.05.1). Unscheduled or unplanned readings will be presented within the participant's listings. 	

 ○ When data falls within both maintenance / extension and long-term follow-up phases, it will be presented in maintenance / extension phase, unless otherwise specified. ○ Unless otherwise specified, when data falls within both screening and baseline visits per analysis visit windows, it will be presented at baseline visit. 	
Unscheduled Visits	

 • Unscheduled visits will be assigned to a study visit using the all-inclusive windows defined in Section 15.3. • However, data summaries will only report visits that are planned assessment time points for each parameter (according to the Time and Events table). • Assessments at unscheduled visits will be included for 'any time On-treatment' time points and in data listings, as well any algorithms that make use of additional data (e.g., Snapshot). 	
Descriptive Summary Statistics	
Continuous Data	Refer to IDSL Statistical Principle 6.06.1
Categorical Data	N, n, frequency, %
Graphical Displays	

 • Refer to IDSL Statistical Principals 7.01 to 7.13. 	

15.5.3. Reporting Standards for Pharmacokinetic

Reporting of Pharmacokinetic Concentration Data	
Descriptive Summary Statistics, Graphical Displays and Listings	
Refer to IDSL PK Display Standards.
 
Refer to IDSL Statistical Principle 6.06.1
 
Assign the low limit of quantification (CAB 0.025 ug/mL, RPV 1 ng/mL) to NQ values.

Reporting of Pharmacokinetic Parameters	
Descriptive Summary Statistics (Log _e Transformed)	
N, n, geometric mean, 95% CI of geometric mean, standard deviation (SD) of log_e transformed data and between participant coefficient of variation (CV_b (%)) will be reported.
 
 ○ $CV_b(\%) = \sqrt{\exp(SD^2) - 1} \times 100$ (SD = SD of log_e transformed data)

15.6. Appendix 6: Derived and Transformed Data

15.6.1. General

Multiple Measurements at One Time Point
 
 If after window assignment there are multiple valid assessments of a parameter within the same window, refer to Section 15.3.6 for determination of the value to be used for summary statistics of observed values. Assessments not chosen for use in summary statistics will still appear in the associated listings. Assessments not chosen for use in summary statistics by this algorithm will still appear in the associated listings. Also, all applicable valid assessments, irrespective of proximity to the target study day, will be used when categorizing values across visits, such as 'maximum grade' or 'at any time', and for any algorithm that has specific rules for which observation to use (e.g. snapshot algorithm, LOCF or CVF identification).

Treatment Start Date
 
Treatment start date is defined as follows:
 
Maintenance Phase
 
 Date of first ATLAS-2M dose of CAB+RPV (oral or injection) entered onto the IP exposure eCRF form. 
Extension Phase
 
 For participants not continuing into extension phase, treatment start date is missing. For participants continuing into extension phase, treatment start date is the date of first dose of CAB+ RPV (oral or injection) at or after nominal Week 100 visit. 
Long-term Follow-up Phase
 
 If a participant is still on study treatment, or permanently discontinued the study treatment and did not have any previous injections, treatment start date is missing. If a participant permanently discontinued the study treatment and had at least one injection, treatment start date is the date of first ART treatment after the last dose of study treatment (oral or injection).

Study Day
 
The Study Day of an event (e.g., lab assessment, vital sign, ECG, start date of AE or HIV associated condition) will be derived as the number of days between the date of the event and the start date of study treatment during the Maintenance Phase as follows:
 
if date of event \geq start date of study treatment, then
 
 Study Day = date of event - start date of Maintenance Phase treatment + 1 
if date of event < start date of study treatment, then
 
 Study Day = date of event - start date of Maintenance Phase treatment 
Note that the start date of study treatment during maintenance phase is considered to be on Study Day 1 and the day before this is Study Day -1; i.e., there is no Study Day 0.

Extension Phase Study Day

The Study Day of an event (e.g., lab assessment, vital sign, ECG, start date of AE or HIV associated condition) will be derived as the number of days between the date of the event and the date of nominal Week 100 visit as follows:
 
if date of event \geq date of nominal Week 100 visit, then
 
 • Study Day = date of event - date of nominal Week 100 visit + 1 
if date of event < date of nominal Week 100 visit, then
 
 • Study Day = date of event - date of nominal Week 100 visit 
Note that the date of nominal Week 100 visit is considered to be on Extension Phase Study Day 1 and the day before this is Extension Phase Study Day -1; i.e., there is no Extension Phase Study Day 0.

Long-term Follow-up Study Day

The Long-Term Follow Up (LTFU) Study Day of an event (e.g., lab assessment, start date of AE or HIV associated condition) will be derived as the number of days between the date of the event and the end of IP treatment [i.e. max(Last IM Injection Date, Last Oral Bridging End Date)] as follows:
 
If the date of event falls in Long-term Follow up phase, then
 
 • LTFU Study Day = Date of Event - End Date of IP
Change from Baseline

 • Post-Dose Visit Value – Baseline 
 ○ Unless otherwise specified, the baseline definitions specified in Section 5.2 will be used for derivations for endpoints / parameters.

15.6.2. Study Population

Demographics and Baseline Characteristics
Age

 • Age, in whole years, will be calculated with respect to the participant's Screening visit. • GSK standard IDSL algorithms will be used for calculating age where birth date will be imputed as follows: 
 ○ Any participant with a missing date and month will have this imputed as '30th June'. • Birth date will be presented in listings as 'YYYY'. • Completely missing dates of birth will remain as missing, with no imputation applied. Consequently, the age of the participant will not be calculated and will remain missing.
Body Mass Index (BMI)

 • Calculated as Weight (kg) / Height (m)²
Hepatitis Status

 • Hepatitis C status will be determined using antibody and/or hepatitis C virus (HCV) RNA assessments performed during screening or during the conduct of the study. • If both antibody and virus RNA assessments are available, then the latter will take precedence and positive/negative status will be based on whether HCV RNA is detectable (i.e., \geq limit of quantification) or not. • A participant will be considered positive for hepatitis B virus (HBV) if they have a positive

Demographics and Baseline Characteristics

surface antigen or detectable HBV DNA result. "HBV DNA DETECTED" in the lab comment takes precedence over HBV DNA test result for positive hepatitis B status, for example, if a participant has HBV test result below level of detection, however, the lab comment shows that HBV DNA detected, this participant will be considered positive for hepatitis B. If HBV DNA result is available, it will be used to qualify hepatitis B status as positive or negative (positive if \geq limit of quantification); otherwise Hepatitis B status will be determined using the surface antigen result.

- Hepatitis status at entry will be based on the assessments prior to/on the start of the study treatment.

Framingham Risk Equation

- The predicted probability, \hat{p} , of having a cardiovascular disease (CVD) within the next 10-years according to the Framingham formula [D'Agostino et al. 2008] is

For females:

Prior Exposure to CAB+RPV

 For participants transitioning from ATLAS study and having prior exposure to CAB+RPV in ATLAS study: Duration of Prior Exposure to CAB+RPV = Randomization Date – Prior Oral CAB Start Date in ATLAS Study + 1. For participants transitioning from ATLAS study and not having prior exposure to CAB+RPV in ATLAS study, or for participants randomized from current SOC, Duration of Prior Exposure to CAB+RPV = 0. Duration of Prior Exposure to CAB+RPV will be categorized to 0 weeks, 1-24 weeks and >24 weeks.
Lipid-modifying Agents

 The following ATC codes correspond to lipid-modifying agents: 
 ATC Level 2: C10 ATC Level 3: C10A, C10B (if Level 2 is not available) ATC Level 4: C10AA, C10AB, C10AC, C10AD, C10AX, C10BA, C10BX (if level 2, 3 are not available) Participants are considered to have used a lipid-modifying agent at baseline if they are taking the medication at the time of their baseline lipid testing date. Participants are also considered to have used a lipid-modifying agent at baseline if they stopped their lipid modifying medication within 12 weeks prior to their baseline lipid testing date.

15.6.3. Efficacy

Snapshot

 The Snapshot algorithm is intended to be primarily a virologic assessment of the endpoint, and as such follows a “virology first” hierarchy. ‘HIV-1 RNA < 50 c/mL’ or ‘HIV-1 RNA ≥ 50 c/mL’ within an analysis window (see Table 10) is typically determined by the last available HIV-1 RNA measurement in that window while the participant is On-treatment in the Maintenance Phase (as assigned based on Section 15.4). When no HIV-1 RNA data is available within a window, a participant cannot be assigned to the category of ‘HIV-1 RNA < 50 c/mL’. Depending on the reason for lack of data, the participant will be classified as ‘HIV-1 RNA < 50 c/mL’ or reported as ‘No Virologic Data at Week X’; in the latter case, the algorithm further classifies the nature of the missing data. Typically, a participant withdrawn (i) due to AE or, (ii) for another reason yet was suppressed at the time, will be counted as ‘No Virologic Data at Week X’. Should a participant withdraw for reasons other than AE and was not suppressed at the time, they will be categorized as ‘HIV-1 RNA ≥ 50 c/mL’. Full details of the algorithm, including the handling of special cases, are included in Section 15.9

Plasma HIV-1 RNA

 For summaries and analyses which use HIV-1 RNA level as a continuous measure, the logarithm to base 10 of the value will be used. HIV-1 RNA results may be provided as censored values, such as <40 or >9,999,999 c/mL. For the purposes of summary statistics, such values will be replaced by the next value beyond the limit of detection, e.g., 39 or 10,000,000 c/mL, respectively, for the given examples. Data listings will show the censored values as provided.
Target Detected / Target Not Detected / Super Low Viral Load Testing

 When a measurement of plasma HIV-1 RNA is below the limit of quantification (i.e. 40 c/mL) and is qualitatively observable that will be denoted as a “Target Detected” measure, while HIV-1 RNA below the limit of quantification that is not qualitatively observable that will be denoted as “Target Not Detected”. Any measurements <40 c/mL characterised as “Target Not Detected” or “Target Detected” will be captured in the database. Super low viral load will also be tested by BioMNTR lab for viral loads below the limit of quantification at some visits (e.g. Week 48).
Confirmed Virologic Failure (CVF)

 The definition of CVF is provided in the Protocol, Section 5.5.4 – Definition of Confirmed Virologic Failure. In case there are multiple plasma HIV-1 RNA results on the same day, the worst result (i.e. the largest value) will be used in determination of CVF.
Treatment (TRDF) and Efficacy Related (ERDF) Discontinuation = Failure

 The analysis of time to confirmed virologic failure (CVF) or discontinuation due to treatment related reasons (i.e., drug-related AE, intolerability of injections, protocol defined safety stopping criteria, or lack of efficacy) will censor participants who have not met CVF criteria and are ongoing in the study, or who have discontinued for reasons other than those related to treatment. This will be the Treatment Related Discontinuation = Failure (TRDF) data. Participants who have not met CVF criteria and are ongoing in the study, or who have discontinued for reasons other than lack of efficacy, will be censored in the analysis of the Efficacy Related Discontinuation = Failure (ERDF) data. Proportion of Participants without virologic (ERDF) or tolerability (TRDF) failure will be estimated using the Kaplan-Meier nonparametric method based on the time to ERDF or TRDF. The estimated proportion at time point of interest will be presented by treatment group, along with estimated difference in proportions between treatment groups and its associated two-sided 95% CI. The estimate of the standard error used to derive confidence intervals will be based on Greenwood’s formula [Kalbfleisch, 1980]. See Appendix 10: Variables Defined for Time to Event Analysis for additional details.
Summary for Participants per Viral Load Category by Visit

 Summary will be based on observed available data, with no imputation for missing values. The proportion of participants in each viral load category will be calculated using the denominator and numerator specified below: 
 Denominator: Number of participants with on-treatment viral load within the snapshot visit window. Numerator: Number of participants with plasma HIV-1 RNA in the specified category based on the last on-treatment viral load assessment collected within the snapshot visit window.

HIV-1 Disease progression Stage

- Categories:
 - CDC Stage I at Baseline to CDC Stage III;
 - CDC Stage II at Baseline to CDC Stage III;
 - CDC Stage III at Baseline to new CDC Stage III event;
 - CDC Stage I, II, III at Baseline to Death.

Please refer to Protocol (Appendix 4: CDC Classification for HIV-1 Infection) for defining Stage.

- For the purpose of analysis, the CDC at Baseline and at post-baseline during Maintenance Phase will be derived as below:
 - At Baseline, the 'Baseline CDC stage' for each participant was assessed by investigator and recorded in the eCRF. However, for the analysis, Baseline CDC stage will be rederived based Baseline CD4+ values as well as whether any HIV-associated/AIDS-defining conditions present at baseline per the Criteria's thresholds (Appendix 4 in Protocol).
 - To analyse disease progression, the most advanced post-baseline CDC stage within the period of interest (e.g. Maintenance Phase) will be derived based on the occurrences of new AIDS-defining conditions (please refer to Appendix 4 in Protocol for the list of AIDS-defining Conditions) as well as the nadir value of post-baseline CD4+.
 - For example, if a participant with CDC 'Stage I' at Baseline had the lowest Maintenance Phase CD4+ =120 cell/mm³ without new AIDS-defining conditions, then HIV disease progression for this participant during the Maintenance Phase would be considered as 'CDC stage I at Baseline to CDC stage III'.
 - If a participant with CDC 'Stage II' at Baseline had the lowest Maintenance Phase CD4+ =220 cell/mm³ AND had at least one new AIDS-defining condition, then HIV disease progression for this participant during the Maintenance Phase would be considered as 'CDC stage II at Baseline to CDC stage III'.

Delay in IP Injection

- For participants on the Q4W arm, IM dosing is expected to occur every 4 weeks from Week 4B onwards for those transitioning from SOC (i.e. those requiring oral lead-in) and from Day 1 onwards for those transitioning from CAB+RPV Q4W in ATLAS (i.e. those not requiring oral lead-in). The Delay in IP injection (days) will be calculated as:
 Delay in IP Injection (days) = Injection date - date of preceding injection - 28 days
- For participants on the Q8W arm, IM dosing is expected to occur at Week 4B and then every 8 weeks from Week 8 onwards for those transitioning from SOC (i.e. those requiring oral lead-in) and every 8 weeks from Day 1 for those transitioning from CAB+RPV Q4W (i.e. those not requiring oral lead-in) in ATLAS.
 - For participants transitioning from SOC on the Q8W arm, if the preceding injection occurs at Week 4B, the Delay in IP injection (days) will be calculated as:
 Delay in IP Injection (days) = Date of Week 8 injection - date of Week 4B injection - 28 days
 - For participants transitioning from SOC on the Q8W arm, if the preceding injection occurs at a visit later than Week 4B, the Delay in IP injection (days) will be calculated as:
 Delay in IP Injection (days) = Injection date - date of preceding injection - 56 days
 - For participants transitioning from CAB+RPV Q4W in ATLAS on the Q8W arm, the Delay in

IP injection (days) will be calculated as:
 Delay in IP Injection (days) = Injection date - date of preceding injection - 56 days

- Delay in IP injection will be grouped into: ≤1, 2-3, 4-7, >7 days.
- The proportion of participants with HIV-1 RNA ≥50 c/mL at Week 48 (Snapshot) will be summarized by last delay in IP Injection. The last delay in IP injection will be the delay in IP injection at Week 48, or the delay in last IP injection prior to Week 48 if a participant did not receive Week 48 injection (i.e. missing visit or withdrawal).

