	
analysis timepoint of interest for Week 48 analysis (i.e. the date of last on-treatment viral load up to Study Day 378): two or more injection intervals affected by over dosage deviations.
 
 • For participants who received injections beyond the analysis timepoint of interest for Week 48 analysis (i.e. the date of last on-treatment viral load up to Study Day 378): three or more injection intervals affected by over dosage deviations. 
3. $\geq 10\%$ of total time on-treatment with under dosing deviations. The percentage of total time on-treatment with under dosing deviations will be calculated by (the total number of non-compliant dosing days / the total number of intended exposure days) * 100%.
 
Number of Intended Exposure Days = Date of Last Viral Load – Start Date of Study Treatment + 1, where the last viral load refers to the last on-treatment viral load up to Study Day 378 during maintenance phase for Week 48 analysis, and the last on-treatment viral load up to Study Day 714 during maintenance phase for Week 96 analysis.
 
The total number of non-compliant dosing days up to the analysis timepoint visit (or date of IP discontinuation/ withdrawal, whichever is earlier), is derived as follows (summing across all instances):
 
 • For Q4W arm participants requiring oral lead-in: 
 ○ Length of time (in days) until next injection from date of dosage deviation (e.g. 2 mL administered instead of 3mL for Week 4B injection, 1ml administered instead of 2 mL for post Week 4B injections). ○ Length of time (in days) in excess beyond 35 days between injections post Week 12 and in excess beyond 28 days for Week 8 and Week 12 (e.g. missed or late injection visit). ○ Length of time (in days) in excess beyond 35 days from last injection until start of oral bridging post Week 12 and in excess beyond 28 days for Week 8 and Week 12. • For Q4W arm participants not requiring oral lead-in: 
 ○ Length of time (in days) until next injection from date of dosage deviation (e.g. 1 mL administered instead of 2 mL). ○ Length of time (in days) in excess beyond 35 days between injections. ○ Length of time (in days) in excess beyond 35 days from last injection until start of oral bridging post Week 12. • For Q8W arm participants requiring oral lead-in: 
 ○ Length of time (in days) until next injection from date of dosage deviation (e.g. 2 mL administered instead of 3mL). ○ Length of time (in days) in excess beyond 63 days between injections post Week 16 and in excess beyond 56 days for Week 8 and Week 16 (e.g. missed or late injection visit). ○ Length of time (in days) in excess beyond 63 days from last injection until start of oral bridging post Week 16 and in excess beyond 56 days for Week 8 and Week 16. • For Q8W arm participants not requiring oral lead-in: 
 ○ Length of time (in days) until next injection from date of dosage deviation (e.g. 2 mL administered instead of 3 mL). ○ Length of time (in days) in excess beyond 63 days between injections. ○ Length of time (in days) in excess beyond 63 days from last injection until

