
Timeliness of Injections relative to Date of Projected Dosing Visits are assessed by using "actual injection visit date - projected visit date from first injection". The injections of interest in adherence analysis are those after first injection. For participants requiring the oral CAB+RPV lead-in, the first injection is planned to be taken at Week 4B. For participants not requiring the oral CAB+RPV lead-in, the first injection is planned to be taken at Baseline/Day 1. Each injection visit is counted only once. Individual CAB and RPV injections administered at the same visit are not counted twice. "Extra" unscheduled injections are excluded from all derivations. For example, if during a scheduled visit a participant receives 1 ml of injection instead of 2 ml due to a dosing error, but this participant returns one week later for the remaining 1 ml injection, then the additional visit is excluded. If a participant receives an extra injection at an unscheduled visit by mistake, this visit will also be excluded.
 
The categories of Timeliness of Injections relative to Date of Projected Dosing Visits for summary are listed below:
 
 < -14 days -14 to -8 days -7 to -4 days -3 to -2 days -1 0 day 1 2 to 3 days 4 to 7 days 8 to 14 days >14 days Missed Injection without Oral Bridging Missed Injection with Oral Bridging
Columbia Suicide Severity Rating Scale (C-SSRS)

 • Missing data will not have any imputation performed (Nilsson et al, 2013).

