15.9. Appendix 9: Snapshot Algorithm Details

Detailed Algorithm Steps		

 • Consider an analysis visit window for Week X as defined in Table 10. • The HIV-1 RNA threshold of 50, 200 c/mL will be analysed, respectively, in this study • The analysis window ‘Week 48’ and HIV-1 RNA threshold of ‘50 c/mL’ are used for the purpose of illustration. A participant’s Snapshot response and reason at Week 48 are categorized as below. 
 ○ HIV-1 RNA < 50 c/mL ○ HIV-1 RNA ≥ 50 c/mL 
 Data in window not below 50 Discontinued for lack of efficacy Discontinued for other reason while not below 50 Change in background therapy* ○ No Virologic Data at Week 48 Window 
 Discontinued study due to AE or death Discontinued study for other reasons On study but missing data in window 
* Note: since permanent change in ART are not permitted in this protocol, all such participants who permanently change ART will be considered ‘HIV-1 RNA ≥ 50 c/mL’ if the permanent change in ART is made prior to an analysis timepoint. Participants with protocol permitted oral bridging treatment or a temporary change in ART prior to an analysis timepoint (e.g. participant took the ART different from study treatment during oral lead-in by mistake for a short period and then went back to the study treatment) will not be considered ‘HIV-1 RNA ≥ 50 c/mL’ due to ‘change in ART’.
 
 • The steps in determining response and reasons are indicated in the table below, in the order stated: 		
Detailed steps		
Please note that the following scenarios will NOT be penalized Per Snapshot algorithm (i.e. please exclude these scenarios from Condition 1-4).		

 • Dose reduction, dropping a component, or change in formulation (e.g. ‘Tivicay + Kivexa’ to ‘Triumeq’ with the identical ingredients) 		
Condition (‘Week 48’ indicates Week 48 window)	Response	Reasons
1. If non-permitted change in background therapy prior to Week 48	HIV-1 RNA ≥ 50	Change in background therapy
2. If permitted change ^[a] in background therapy prior to Week 48 AND the latest on-treatment VL prior to/on the date of change is ≥ 50 c/mL (NA to this study)	HIV-1 RNA ≥ 50	Change in background therapy

3. If non-permitted change in background therapy during Week 48		

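### The delay-in-injection variable ignores oral bridging, so the top delay group in Table 2.21 can pool orally covered intervals with uncovered ones

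*SAP*

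**What the plan says.** SAP Section 15.6.3 (Delay in IP Injection) defines the variable by arm. For Q4W it is "Delay in IP Injection (days) = Injection date - date of preceding injection - 28 days". For Q8W it is "Delay in IP Injection (days) = Injection date - date of preceding injection - 56 days", except that the interval from Week 4B to Week 8 after an oral lead-in is measured against 28 days. The grouping rule is "Delay in IP injection will be grouped into: ≤1, 2-3, 4-7, >7 days".

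Only one interval per participant enters: "The last delay in IP injection will be the delay in IP injection at Week 48", or the delay of the last earlier injection if there was no Week 48 injection. The Week 48 Snapshot proportion with HIV-1 RNA ≥50 c/mL "will be summarized by last delay in IP Injection". The output is Table 2.21 (Section 15.14.5.2), repeated for Week 96.

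None of these rules has a term, exclusion or category for oral bridging. Note 6 to Table 3 (Section 7.3) only points back to 15.6.3, and the programming note for Table 2.21 adds no bridging rule.

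Bridging is recognised elsewhere in the SAP:
- The adherence summary in Section 15.6.4 has a category "Missed Injection with Oral Bridging", next to one for misses without bridging.
- The per-protocol under-dosing rule in Section 15.1.1 (criterion 02) counts, for Q4W, days "in excess beyond 35 days from last injection until start of oral bridging", with a 63-day counterpart for Q8W.
- Section 15.9 says that "Participants with protocol permitted oral bridging treatment or a temporary change in ART prior to an analysis timepoint" are not made failures on that ground, so bridged participants remain in Table 2.21 and are judged on their viral load.

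**The concern.** A reader will naturally use Table 2.21 to see whether virologic failure is more common after late injections. Its top group should then hold participants whose drug cover ran past the planned interval. As defined, it also takes in participants who took oral CAB+RPV during the gap, and nothing in the title, the prescribed footnote or the grouping says so.

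A failure rate for that group cannot be attributed to late dosing without cover, because it averages over two kinds of exposure in unknown proportions. What is at stake is how one exploratory table is read. No hypothesis test depends on it.

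**Working it through.** The SAP gives no numerical result for this analysis, so there is no figure to reproduce. The check applies the plan's own formulas to a bridged interval.

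**Inputs from the SAP.** Planned intervals are 28 days (Q4W) and 56 days (Q8W, after Week 8 or without oral lead-in). The top group is more than 7 days (Section 15.6.3). The under-dosing allowances are 35 and 63 days, or 28 and 56 days for the early visits after an oral lead-in (Section 15.1.1).

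**Step 1: one scheduled injection replaced by bridging, injections resumed at the next scheduled visit.**
- Q4W: Week 44 missed, injections at Weeks 40 and 48. The gap is 56 days and the delay is 56 − 28 = 28 days.
- Q8W: Week 40 missed, injections at Weeks 32 and 48. The gap is 112 days and the delay is 112 − 56 = 56 days.

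With two replaced injections the delays are 84 − 28 = 56 days and 168 − 56 = 112 days. All four fall in the top group.

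**Step 2: the same interval under the per-protocol rule.** If bridging starts on the due date, the time from last injection to start of bridging is 28 days (Q4W) or 56 days (Q8W). The excess over the allowance is max(0, 28 − 35) = 0 and max(0, 56 − 63) = 0. With the stricter 28- and 56-day limits it is also 0. So an interval that adds no days to the under-dosing count before bridging starts scores 28 or 56 days of delay in Section 15.6.3.

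**Step 3: when this reaches the table.** Only the last delay at or before Week 48 counts.
- An earlier bridge, followed by further injections up to Week 48, does not enter.
- A participant still on a bridge at Week 48 without a Week 48 injection is classed by the preceding injection's delay, which may be small.
- A bridge that postpones the injection by 7 days or less falls in a lower group.

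**Step 4: possible effect, under assumed rates.** Let f be the bridged share of the top group. Then

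rate shown = (1 − f) × rate if late without cover + f × rate if bridged.

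Assume 1% failure when on time, 5% when late without cover and 1% when bridged:
- f = 0: 5.0%
- f = 25%: 0.75 × 5 + 0.25 × 1 = 4.0%
- f = 50%: 0.50 × 5 + 0.50 × 1 = 3.0%
- f = 75%: 0.25 × 5 + 0.75 × 1 = 2.0%

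With the on-time rate held at 1%, f = 50% and a bridged rate of 0% or 1%, the ratio to on-time falls from 3.0 to 1.5–2.0 if the uncovered late rate is 3%. It falls from 10.0 to 5.0–5.5 if that rate is 10%. If bridged participants fail as often as uncovered late ones, for example both at 5%, the rate shown is 0.5 × 5 + 0.5 × 5 = 5% and there is no dilution. All these rates and shares are assumptions; the SAP supplies none of them.

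**The case against.** The strongest reply is that the variable does what its name says. It measures injection timing against planned spacing, and a participant who resumes injections after a bridge has in fact had a late injection. The per-protocol rule and the adherence summary serve other purposes: one counts under-dosed days for exclusion, the other compares visits with projected dates and still labels a bridged miss as missed. A reader might infer that the plan contradicts itself by treating the same days as covered in one place and uncovered in another. The text does not support that, because Section 15.6.3 never calls the interval uncovered. What remains is that the plan draws this distinction elsewhere and does not draw it in the table where failure is set against delay.

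A reader might also infer that every bridged participant lands in the top group, or that the link between delay and failure is certainly weakened by a calculable amount. Neither follows. Step 3 of the working shows how narrow the route into the table is. The direction depends on bridged participants failing less often than uncovered late ones. The SAP does not say this, and its per-protocol rule allows for interruptions of three or more consecutive days during bridging.

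The Week 48 package also lists exposure for bridged participants (Listing 60) and participants with viral load ≥50 c/mL (Listing 41), and it gives the adherence summary (Table 3.4). A careful reader could identify the bridged participants by cross-reference. That lessens the problem but does not change what Table 2.21 displays.

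**Conclusion.** The point holds as a minor weakness in one exploratory table. When the last injection at or before Week 48 ends an interval in which a scheduled injection was fully replaced by permitted bridging, the participant is recorded as 28 days (Q4W) or 56 days (Q8W) late and pooled with participants who were late without oral cover. That mixing follows from the formulas.

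Dilution of the failure rate shown for late injections is conditional on bridged participants failing less often than unbridged late ones. Its size cannot be estimated from the SAP, so the percentages in the working illustrate the mechanism and forecast nothing. The primary non-inferiority comparison and the key secondary comparisons do not use this variable and are unaffected.

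**What to change.** In Section 15.6.3 and the programming note for Table 2.21, add a separate category, in both arms, for a last interval covered by oral bridging, as Section 15.6.4 already does for missed injections. Keep the four delay groups for the remaining participants. The same sentence should state how a bridge still running at Week 48 is classed, since the present rule falls back on the preceding injection. Carry the change to the Week 96 version.

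Subtracting bridged days from the delay is the less suitable option. It would move participants with gaps of 56 or 112 days between injections into the group of at most 1 day, and so mix exposures in the on-time group instead.

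The cost is one sentence, a small program change and one more row that is likely to be sparse. Bridging start and end dates are already used in other derivations (Sections 15.1.1 and 15.6.1), so no new data are needed. The change concerns the analysis definition only and touches no dosing or bridging rule.
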